7.5.2 Adverse Events

The AEs will be coded by the latest version of MedDRA. The toxicity of AEs will be graded using National Cancer Institute Common Terminology for Adverse Events (NCI CTCAE) v5.0.

All AEs will be categorized according to the safety analysis periods (refer to Section 7.2.4), ie. pre-treatment safety period, treatment safety period, and follow-up safety period:

- Pre-treatment AEs, ie, those with imputed AE onset dates falling within the pre-treatment safety period.
- Treatment-emergent adverse event (TEAEs), ie, those with imputed AE onset dates falling within the treatment safety period. See Section 7.2.1 for AE onset date imputation.
- Follow-up AEs, i.e., those with imputed AE onset dates falling within the follow-up safety period.

Drug-related AEs are the AEs assessed by the site investigator as having a relationship to the investigational product of "definitely related", "probably related", or "possibly related".

An overall summary of AEs will display the number and percentage of participants reporting the following AEs for participants in different categories of average rimegepant exposure (< 2 , ≥ 2 to < 8 , ≥ 8 to < 14 , < 14 and ≥ 14 tablets per month) and overall participants for treatment safety and follow-up safety analysis periods, respectively, as below:

- For treatment safety analysis period, the following will be summarized using SS:
 - Any TEAE, any drug-related TEAE,
 - Any serious TEAE, any drug-related serious TEAE,
 - Any TEAE with CTCAE grade ≥ 3 , any drug-related TEAE with CTCAE grade ≥ 3 ,
 - Any TEAE leading to drug interruption; any drug-related TEAE leading to drug interruption,
 - Any TEAE leading to treatment discontinuation, any drug-related TEAE leading to treatment discontinuation,
 - Any TEAE leading to study discontinuation, any drug-related TEAE leading to study discontinuation,
 - Any TEAE leading to death, any drug-related TEAE leading to death.

- For follow-up safety analysis period, the following will be summarized using FUSS:
 - Any AE,
 - Any SAE,
 - Any AE leading to death.

Further, the number and percentage of participants with the following AEs will be tabulated by SOC and PT for participants in different categories of average rimegepant exposure (< 2 , ≥ 2 to < 8 , ≥ 8 to < 14 , < 14 and ≥ 14 tablets per month) and overall participants for treatment safety and follow-up safety analysis periods, respectively, as below:

- For treatment safety analysis period, the following will be summarized using SS:
 - TEAEs,
 - Drug-related TEAEs,
 - Serious TEAEs,
 - Drug-related serious TEAEs.
- For follow-up safety analysis period, the following categories will be summarized using FUSS:
 - AEs,
 - Serious AEs.

In addition, the number and percentage of participants with the following AEs will be tabulated by SOC, PT, and maximum CTCAE grade (Grade 1, 2, 3, 4, 5, ≥ 3 , ≥ 4) for participants in different categories of average rimegepant exposure (< 2 , ≥ 2 to < 8 , ≥ 8 to < 14 , < 14 and ≥ 14 tablets per month) and overall participants for treatment safety and follow-up safety analysis periods, respectively, as below:

- For treatment safety analysis period, the following will be summarized using SS:
 - TEAEs,
 - Drug-related TEAEs.
- For follow-up safety analysis period, the following categories will be summarized using FUSS:
 - AEs.

For the above AE tables that display CTCAE toxicity grade, if the same AE is reported by the same participant repeatedly, the AE with the highest NCI-CTC grade (Grade 5 > Grade 4 > Grade 3 > Grade 2 > Grade 1 > Missing) will be presented in the summary table. The participants will be counted once according to the highest grade under each unique PT item in the SOC.

Participants reporting the following AEs will be listed separately using SS:

- AEs with CTCAE Grade ≥ 3 ,
- AEs leading to treatment discontinuation,
- AEs leading to study discontinuation,
- AEs leading to death,
- AEs Leading to drug Interruption.

All AEs will be listed by participant ID with a flag indicating each AE to be a pre-treatment AE, a TEAE, or a follow-up AE.

A death listing for all the screened participants will be generated.

7.5.3 Clinical Laboratory Tests

The clinical laboratory evaluation results collected by the central laboratory will include:

(1) Clinical safety laboratory tests

Hematology: hemoglobin, hematocrit, red blood cell count, white blood cell counts with differential count, and platelets.

Chemistry: sodium, potassium, chloride, bicarbonate, calcium; glucose, HbA1c, BUN (urea), serum creatinine, uric acid, lactate dehydrogenase (LDH), total protein, albumin, creatine phosphokinase (CPK) (with fractionation test, if CK result is $> 1.5 \times \text{ULN}$), estimated glomerular filtration rate (eGFR) using the estimated modification of diet in renal disease (MDRD) formula (calculated at central lab), aspartate transaminase (AST), alanine transaminase (ALT), Alkaline Phosphatase (ALP) and Bilirubin (Total, Direct, Indirect).

(2) Blood lipid test: cholesterol, low-density lipoprotein, high-density lipoprotein, triglyceride.

(3) Urinalysis: pH, specific gravity, ketones, nitrite, urobilinogen, leukocyte esterase, protein, glucose, and occult blood. Microscopic examination will be performed if occult blood, protein or white blood cells are positive.

(4) FSH: for WOCBP at screening visit to determine WOCBP status.

Results from central and local laboratory tests will be summarized. For local laboratory parameters with different units from the central laboratory, the results will be converted. Results cannot be converted will be included in the listing.

For the continuous hematology, chemistry, and blood lipid laboratory test parameters, observed values and changes from baseline will be summarized at the following timepoints: baseline, each scheduled visit, early termination, and Follow-up visit using the SS.

Summaries will be performed using central laboratory results if both central and local laboratory parameters are collected at a visit. If there are multiple values collected at the same

visit, rule stated in Section 7.2.2 will be applied.

The number and percentage of participants with laboratory test abnormalities according to CTCAE grade (Grade 0; Grade 1-2; Grade 3-4) will be presented during the treatment (using SS) and follow-up (using FUSS) safety analysis periods, respectively. The highest CTCAE grade during the analysis period will be used. Additionally, the abnormal laboratory tests in at least 5% of overall participants or CTCAE Grade 3-4 will be summarized by average rimegepant exposure (< 2, \geq 2 to < 8, \geq 8 < 14, < 14, \geq 14 tablets per month, and overall).

The number and percentage of participants with shifts from baselines in CTCAE grades (Grade 0, 1, 2, 3, 4, 1-4) to the treatment safety period based on SS (refer to Section 7.2.4) will also be presented, using the highest CTCAE grade.

The number and percentage of participants with LFT elevations in the following categories will be presented during the treatment based on SS safety analysis period, for participants in different categories of average rimegepant exposure (< 2, \geq 2 to < 8, \geq 8 < 14, < 14 and \geq 14 tablets per month) and overall participants:

- Cumulative elevations

ALT > 1x, \geq 3x, \geq 5x, \geq 10x, and \geq 20x ULN

AST > 1x, \geq 3x, \geq 5x, \geq 10x, and \geq 20x ULN

ALT or AST > 1x, \geq 3x, \geq 5x, \geq 10x, and \geq 20x ULN

TBL > 1x and \geq 2x ULN

ALP > 1.5x ULN

These are based on the highest ratio of value to ULN for each laboratory test. Note that participants may be in > 1 category for each laboratory test.

- Mutually exclusive elevations

ALT > ULN to \leq 3x ULN, \geq 3x ULN to \leq 5x ULN, \geq 5x ULN to \leq 10x ULN, \geq 10x ULN to \leq 20x ULN, and \geq 20x ULN

AST > ULN to \leq 3x ULN, \geq 3x ULN to \leq 5x ULN, \geq 5x ULN to \leq 10x ULN, \geq 10x ULN to \leq 20x ULN, and \geq 20x ULN

These are based on the highest ratio of value to ULN for each laboratory test. Note that participants may be in only 1 category for each laboratory test.

- Composite elevations

ALT or AST > 3x ULN and TBL > 1.5x ULN. This is based on the highest ratio of value to ULN for each laboratory test.

ALT or AST > 3x ULN and TBL > 2x ULN. This is based on the highest ratio of value to

ULN for each laboratory test.

The number and percentage of participants with shifts in LFT elevations from baseline to the treatment safety period using SS (refer to Section 7.2.4) will also be presented according to the greatest elevation; categories for ALT and AST are \leq ULN, $>$ ULN to $\leq 3 \times$ ULN, $> 3 \times$ ULN to $\leq 5 \times$ ULN, $> 5 \times$ ULN to $\leq 10 \times$ ULN, $> 10 \times$ ULN to $\leq 20 \times$ ULN, and $> 20 \times$ ULN.

All laboratory data will be listed using SS. For a given graded laboratory test, the listing displays all test results over time for participants with a CTCAE Grade 3 to 4 laboratory test abnormality at any time point. For a given pregnancy test, the listing also displays all test results over time for participants with a positive pregnancy test result at any time point, defined as a serum or urine pregnancy test with “positive” character value.

The scatter plot of evaluation of Drug-Induced Serious Hepatotoxicity (eDISH) during the study using SS will display the maximum ratio of total bilirubin level divided by ULN on the y-axis versus the maximum ratio of ALT level divided by ULN on the x-axis, where the maxima are in the same study period but not necessarily concurrent. Both axes are on the \log_{10} scale with minima of 0.1. Ratios $< 0.1 \times$ ULN are set to 0.1. A horizontal reference line is placed at $2 \times$ ULN, and a vertical reference line is placed at $3 \times$ ULN. The lower left quadrant is labeled “Normal Range”, the upper left quadrant is labeled “Hyperbilirubinemia”, the lower right quadrant is labeled “Temple’s Corollary”, and the upper right quadrant is labeled “Possible Hy’s Law Range.” A footnote specifies that “Ratios $< 0.1 \times$ ULN are set to 0.1.” and is displayed only if ≥ 1 participant has a ratio set to 0.1.

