6 ANALYSIS SETS

The following analysis sets will be determined:-

- Screened participants set: All participants who sign the informed consent. It will be used for the analysis of participant disposition.
- Enrolled participants set: Participants with an available date collected in the CRF on

which the investigator judges that they can be enrolled and notifies of their eligibility to start taking the investigational product by phone. It will be used for the analysis of participant disposition and drug accountability.

- Full analysis set (FAS): All participants who are enrolled and received at least one dose of the investigational product. It will be used for the analysis of baseline characteristics, as well as the analyses of exploratory endpoint measures.
- Efficacy analysis set (EAS): All participants in the FAS with ≥ 14 eDiary days (not necessarily consecutive) in both the OP analysis period and ≥ 1 month (4-week interval) of the LTT analysis period. The EAS will be used to assess the secondary endpoint.
- Safety analysis set (SS): All participants who received at least one dose of investigational product. The SS will be used for safety analyses during treatment safety period.
- Follow-up safety analysis set (FUSS): All participants in the SS with last contact date (see [Section 7.2.3](#)) in the follow-up safety analysis period. The FUSS will be used for follow-up safety analyses.

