7.2.4 Analysis Periods

To facilitate the analyses based on eDiary data (including eDiary compliance and migraine days), the analyses for safety endpoints, the following analysis periods will be defined.

Table 1. Analysis Periods

Analysis periods	Start date/time	End date/time	Usage
OP	Screening Visit date	LT _T start date – 1 day	To be used to calculate the eDiary compliance, number of migraine days per 4 weeks in this period.
LT _T	Earlier of (1) Baseline Visit date, and (2) study drug start date	Later of (1) Week 52/EOT date, and (2) study drug last dose date	To be used to calculate the eDiary compliance and number of migraine days per 4 weeks or the overall period in the long-term treatment.
Pre-treatment safety		Study drug start date – 1 day for AEs; study drug start date/time otherwise	To be used to assess the safety endpoints prior to study drug treatment.
Treatment safety	Study drug start date for AEs; after study drug start date/time otherwise	[Later of (1) Week 52/EOT date, and (2) study drug last dose date] + 7 days	To be used to assess the safety endpoints of the treatment period.
Follow-up safety	[Later of (1) Week 52/EOT date, and (2) study drug last dose date] + 8 days		To be used to assess the safety endpoints of the follow-up period.

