7.5 Safety Analyses

Safety analyses during the pre-treatment, treatment safety analysis periods will be summarized based on the SS. Safety analyses for follow-up safety period will be summarized based on FUSS.

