7.5.4 Vital Signs and Physical Measurements

For each vital sign parameter (systolic blood pressure, diastolic blood pressure, pulse rate, respiratory rate, temperature) and physical measurement parameter (weight, BMI), observed values and changes from baseline will be summarized at the following timepoints: baseline, each scheduled visit, early termination, and Follow-up visit using SS. See Section 7.2.2 for handing multiple values in an analysis window.

The number and percentage of participants with vital sign abnormalities in the following categories will be presented during the treatment (using SS) and follow-up (using FUSS) safety analysis periods, respectively, for participants in different categories of average rimegepant exposure (< 2 , ≥ 2 to < 8 , ≥ 8 to < 14 , < 14 and ≥ 14 tablets per month) and overall participants:

Individual listing will be provided using SS.

Systolic BP (mm Hg)	min. < 90	
Systolic BP (mm Hg)	max. > 140	
Systolic BP (mm Hg) change from baseline	max. decrease ≥ 30	max. increase ≥ 30
Diastolic BP (mm Hg)	min. < 50	
Diastolic BP (mm Hg)	max. > 90	
Diastolic BP (mm Hg) change from baseline	max. decrease ≥ 20	max. increase ≥ 20
Pulse rate (beats/min)	min. < 40	max. > 120

7.5.5 12-lead ECG

For each 12-lead ECG parameter (heart rate, PR interval, QRS duration, QT interval, and QTcF), the observed values and changes from baseline will be summarized at the following timepoints: baseline, each scheduled visit, early termination, and Follow-up visit using SS. See Section 7.2.2 for handing multiple values in an analysis window.

The number and percentage of participants with ECG abnormalities in the following categories will be presented during the treatment safety (using SS) and follow-up (using FUSS) safety analysis periods, respectively, for participants in different categories of average rimegepant exposure (< 2, \geq 2 to < 8, \geq 8 < 14, \geq 14 and \geq 14 tablets per month) and overall participants:

- QTcF (msec): \leq 450, 450 - \leq 480, 480 - \leq 500, $>$ 500
- QTcF increase from baseline (msec): \leq 30, 30 - \leq 60, $>$ 60.

Individual listing will be provided using SS.

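### SAP 7.5.3 counts LFT elevation categories for the treatment safety period only, so the scheduled follow-up liver tests normally fall outside these counts

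*SAP*

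**What the plan says.** SAP 7.5.3 sets out three families of liver function categories: cumulative multiples of ULN, mutually exclusive bands, and composites of ALT or AST with total bilirubin. It presents "LFT elevations in the following categories will be presented during the treatment based on SS safety analysis period". No follow-up version is specified.

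SAP 7.2.4 ends the treatment safety period at "Later of (1) Week 52/EOT date, and (2) study drug last dose date] + 7 days"; the follow-up safety period begins the next day. SAP 6 creates a separate population for the later period ("The FUSS will be used for follow-up safety analyses"), and SAP 7.5 repeats this ("Safety analyses for follow-up safety period will be summarized based on FUSS").

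The neighbouring abnormality tables use both periods:
- CTCAE laboratory grades (SAP 7.5.3): "will be presented during the treatment (using SS) and follow-up (using FUSS) safety analysis periods".
- Vital sign abnormalities (SAP 7.5.4): "during the treatment (using SS) and follow-up (using FUSS) safety analysis periods, respectively, for participants in different categories of average rimegepant exposure".
- ECG abnormalities (SAP 7.5.5): "during the treatment safety (using SS) and follow-up (using FUSS) safety analysis periods".

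Protocol 10.5.2 promises counts and percentages of LFT elevations in categories fixed in advance, and names no period. Protocol 6.1.4.1 puts AST, ALT, ALP and bilirubin in the safety panel that is drawn at the follow-up visit.

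**The concern.** Laboratory abnormalities are part of the primary endpoint, and LFT elevation is the one organ-specific laboratory summary that the protocol names. Protocol 5.3 excludes people with ALT, AST or bilirubin above ULN (one repeat is allowed for values up to 1.5 times ULN). An elevation at follow-up has therefore arisen since eligibility was checked.

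The trial schedules and pays for a liver panel about two weeks after EOT. Under SAP 7.5.3 as written, an elevation that first appears at that draw, or first crosses a category threshold there, would not be in the table a reader consults for liver safety. The SAP gives no reason for treating these categories differently from the CTCAE, vital sign and ECG categories.

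**Working it through.** The plan states no figure for this point, so the check is one of dates and then of coverage.

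**Inputs**
- End of treatment safety period: max(EOT, last dose) + 7 days (SAP 7.2.4, Table 1).
- Start of follow-up safety period: max(EOT, last dose) + 8 days (same table).
- Follow-up visit: EOT + 14 ± 2, that is EOT + 12 to EOT + 16 (Protocol 4.3, Table 1).
- No drug is dispensed at Week 52 (Protocol 4.3, Table 1, footnote 8), and unused drug is handed back at the EOT visit (Protocol 4.3.3).

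**Step 1: last dose on or before EOT.** The treatment period ends at EOT + 7. The earliest in-window follow-up draw is EOT + 12. Since 12 > 7, every in-window draw (days 12 to 16) lies in the follow-up period.

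**Step 2: last dose after EOT.** The draw counts as treatment only if visit day ≤ last-dose day + 7, so last-dose day ≥ visit day − 7.

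| Follow-up visit (days after EOT) | Last dose needed (days after EOT) |
|---|---|
| 12 | 12 − 7 = 5 or later |
| 13 | 6 or later |
| 14 | 7 or later |
| 15 | 8 or later |
| 16 | 16 − 7 = 9 or later |

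Given the dispensing and return rules, such late dosing should be rare.

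**Step 3: what else shows the follow-up draw.**

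| Output | Follow-up draw included? | Gives counts by multiple of ULN or ALT/AST-with-bilirubin? |
|---|---|---|
| LFT categories (7.5.3) | No, except as in step 2 | Yes |
| LFT shift table (7.5.3) | No, except as in step 2 | ALT and AST bands only |
| CTCAE grade table (7.5.3) | Yes, on FUSS | No: Grades 0, 1-2 and 3-4, test by test |
| By-visit summary (7.5.3) | Yes | No: values and changes; the last value is kept if a test is repeated at a visit (7.2.2) |
| Follow-up AE tables (7.5.2) | If reported as an AE | No |
| Listings, including all results of a test for anyone with a Grade 3-4 value on it | Yes | No counts |
| eDISH plot (7.5.3) | Unclear | No counts; plots ALT and bilirubin ratios, not AST |

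The eDISH description refers to the study as a whole, but also says that the two maxima come from the same study period, without saying which period or periods are plotted.

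**Step 4: size.** One participant is 1/240 = 0.42 percentage points if 240 are analysed. The documents give no rate for elevations first seen at follow-up, so no expected number can be calculated.

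**The case against.** The strongest case is that this is a display choice.

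- **No rule is broken.** Protocol 10.5.2 names no period. The sentence in SAP 7.5 fixes the population for follow-up analyses; it does not require a follow-up twin for every table. A reader might infer a breach of the protocol or of the SAP's own rule, and the documents do not support that. This stands.
- **Other follow-up outputs are also reduced.** The follow-up AE overview has only any AE, SAE and death, and both the CTCAE and LFT shift tables cover treatment only. This stands, and it weakens the contrast. Still, among the tables that count participants in abnormality categories, the LFT table is the one without a follow-up count.
- **A treatment-only count is a reasonable on-treatment estimate.** Seven days is 168 hours, against the 66 hours after last dose that Protocol 8.11.1 uses for collecting pregnancy details. This supports keeping the treatment table as it is. It is not a reason to leave the later draw uncounted.
- **Follow-up elevations can be seen elsewhere.** A reader might infer that a late liver signal would be hidden. It would not be: a Grade 3-4 value triggers a listing of all that participant's results for the test, and clinically significant abnormalities are AEs (Protocol 8.1) that are tabulated for follow-up. The eDISH plot may also cover the period. What these outputs lack is the count.
- **The wording is garbled, so the intent is inferred.** True, but this is itself a reason to repair the sentence.

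**Conclusion.** The point holds as a modest reporting gap. On the only reading that fits SAP Table 1, the cumulative, mutually exclusive and composite LFT counts leave out the scheduled follow-up draw unless dosing continued at least 5 to 9 days past EOT. No other planned table supplies counts by multiple of ULN, or joint ALT/AST-with-bilirubin counts, for that draw; they would have to be derived from the listings.

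The conclusion assumes that the follow-up visit takes place in its window and that drug is returned at EOT as the protocol requires. It does not say that liver risk is understated: the number affected may be zero, and nothing in the documents allows an estimate. It is a cheap improvement to the SAP.

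**What to change.** In SAP 7.5.3:

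1. Rewrite the garbled sentence so that it names the treatment safety analysis period and the SS.
2. Add counts for the follow-up safety period on the FUSS for the cumulative, mutually exclusive and composite categories, using each test's highest ratio to ULN within that period. Overall participants are enough. If parity with the vital sign and ECG tables is wanted, split by exposure category as well.
3. Leave the treatment table and its 7-day window unchanged.
4. State which analysis period or periods the eDISH plot covers.

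The cost is modest programming on data already collected. It is one extra column per table for overall participants, or six (five exposure categories plus overall) at full parity. The only other consequence is that any follow-up elevations become a visible count; the treatment-period figures do not change.

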###### **1. Clinical Safety Laboratory Tests:**

Hematology: hemoglobin, hematocrit, red blood cell count, white blood cell count with differential count, and platelets;

Chemistry: Sodium, potassium, chloride, bicarbonate, calcium; glucose, HbA1c, BUN (urea), serum creatinine, uric acid, lactate dehydrogenase (LDH), total protein, albumin, creatine phosphokinase (CPK) (with fractionation test, if CK result is  $>1.5 \times$  ULN), eGFR using the estimated MDRD formula (calculated at central lab), AST, ALT, ALP and bilirubin (Total, Direct, Indirect);

2. Blood lipid test: cholesterol, low-density lipoprotein, high-density lipoprotein, triglyceride;
3. Urinalysis: pH, specific gravity, ketones, nitrite, urobilinogen, leukocyte esterase, protein, glucose and occult blood. Microscopic examination will be performed if occult blood, protein or white blood cells are positive;
4. FSH: for WOCBP at Screening Visit to determine WOCBP status;

Clinical safety laboratory tests will be performed at the Screening Visit, at the Baseline Visit, at scheduled site visits (Weeks 4, 8, 12, 16, 28, 40, 52, or early termination), and at the Safety follow up Visit as specified in Table 1; lipid panel tests will be performed at the Baseline Visit, at scheduled site visits (Weeks 28, 52, or early termination); urinalysis will be performed at the Screening Visit, at the Baseline Visit, and at scheduled site visits (Week 52 or early termination); and FSH is used by the study to determine WOCBP status at the Screening Visit as appropriate.

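### SAP 7.5.3 composite liver-test rows pair peaks from any time on treatment, so they are a screen and not a count of concurrent elevations; separately, the exclusive ALT/AST classes overlap at their limits

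*SAP*

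**What the plan says.** SAP 7.5.3 summarises liver function elevations in the treatment safety period, overall and by average exposure category. It has two composite rows. The rule for one begins "ALT or AST > 3x ULN and TBL > 2x ULN. This is based on the highest ratio of value to"; the denominator is the upper limit of normal, taken separately for every test. The other row has the same form, with bilirubin above 1.5x instead of 2x. SAP 7.2.4 ends the treatment safety period at "Later of (1) Week 52/EOT date, and (2) study drug last dose date] + 7 days".

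For the eDISH plot the SAP states the timing openly: "where the maxima are in the same study period but not necessarily concurrent". The plot puts "the maximum ratio of ALT level divided by ULN on the x-axis", with reference lines at 3x ULN for ALT and 2x ULN for bilirubin.

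The ALT and AST classes headed as mutually exclusive are closed at both ends. The top two, for example, are "\geq 10x ULN to \leq 20x ULN, and \geq 20x ULN". The accompanying note says: "Note that participants may be in only 1 category for each laboratory test". The shift table later in the same section classifies the same tests with non-overlapping limits (> 3x, > 5x, > 10x, > 20x).

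Protocol 6.1.4.1 puts ALT, AST and bilirubin in one chemistry panel, taken during and after treatment "at scheduled site visits (Weeks 4, 8, 12, 16, 28, 40, 52, or early termination), and at the Safety follow up Visit".

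**The concern.** A reader of a row that joins ALT/AST and bilirubin will tend to assume that both were raised together. The rule does not require this. The trial has one arm, so there is no control group to show how many coincidental pairs to expect. Laboratory abnormalities are part of the primary endpoint (SAP 4.1), and the rows are further split by exposure category, so even one case would be noticed. If its timing is examined only after it appears, that judgement is made post hoc.

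The class limits are a different matter. As written, a participant whose highest ratio is exactly 3, 5, 10 or 20 x ULN belongs to two classes that the SAP says cannot both apply.

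**Working it through.** The plan states no figure on this point, so there is none to reproduce. The check applies the rules as written.

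**1. Composite rule on an example.** A participant has ALT 3.5x ULN at Week 4 only and bilirubin 2.2x ULN at Week 52 only.
- SAP rule: max ALT 3.5 > 3 and max TBL 2.2 > 2, so the participant is counted.
- Same-visit rule: no visit has both criteria met, so the participant is not counted.

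**2. Direction of the error.** If both criteria are met on one date, each period maximum is at least as high as that date's value, so the SAP rule is met too. The any-time count is therefore never below the concurrent count.

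**3. Room for non-concurrent pairs.** Scheduled samples in the period are at Weeks 4, 8, 12, 16, 28, 40 and 52, which makes 7. The follow-up visit is 14 ± 2 days after EOT, so at least 12 days, and falls after the + 7 day cut when the last dose is not later than EOT. The SAP rule accepts 7 × 7 = 49 pairs of an ALT/AST visit with a bilirubin visit. Of these, 7 are same-visit and 42 are not. The widest gap is 52 − 4 = 48 weeks.

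**4. Scale, for illustration only.** The documents give no event rates. Every rate below is assumed, with independence between tests, and N = 240 is taken from SAP 3.4.

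*By participant.* Let a be the chance of ALT/AST > 3x at any time and b the chance of an unrelated bilirubin peak at any time. Then P(at least one chance pair) = 1 − (1 − ab)^240.

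| Row | a | b | Result |
|---|---|---|---|
| TBL > 2x | 1% | 0.5% | 1.2% |
| TBL > 2x | 2% | 1% | 4.7% |
| TBL > 1.5x | 1% | 2% | 4.7% |
| TBL > 1.5x | 2% | 3% | 13.4% |

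These figures include chance pairs that fall on the same date, which a concurrent row would still count.

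*By visit.* Let p and q be the per-visit chances of unrelated ALT/AST > 3x and TBL > 2x, each between 0.2% and 1%, with visits independent.
- Any-time expected count: 240 × [1 − (1 − p)^7] × [1 − (1 − q)^7]. This gives 0.05 at the low end and 1.11 at the high end.
- Same-visit expected count: 240 × [1 − (1 − pq)^7]. This gives 0.007 and 0.17.
- Ratio: 6.6 to 6.9.

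The high end is generous. It implies that 1 − 0.99^7 = 6.8% of participants have an unrelated peak on each test. Elevations that last over several visits would bring the two counts closer together.

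**5. Class limits at an exact tie (ALT or AST ratio = 3).**

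| Summary in SAP 7.5.3 | Where a ratio of exactly 3 falls |
|---|---|
| Cumulative (≥ 3x) | counted |
| Exclusive (≤ 3x, then ≥ 3x) | two classes |
| Composite (> 3x) | not counted |
| Shift table (> ULN to ≤ 3x) | the lower class only |

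The exclusive classes overlap in the same way at 5, 10 and 20. Ratios off the limits, such as 2.9 and 3.1, fall in one class. Bilirubin has a similar mismatch: a ratio of exactly 2 is in the cumulative row (≥ 2x) but not in the composite (> 2x).

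**The case against.** The any-time rule is a disclosed choice. The SAP states it under both composite rows and says of the eDISH maxima that they need not be concurrent. It is conservative, since it can only over-count. All laboratory data are listed (SAP 7.5.3), including unscheduled results (SAP 7.2.2), so the timing of a rare case can be read from the listing. The analysis is descriptive, and no threshold or decision hangs on the count. Protocol 5.3 excludes Gilbert's syndrome, active hepatic or biliary disorders, and ALT, AST or bilirubin above ULN (with one repeat allowed between 1 and 1.5x ULN), so unrelated bilirubin peaks should be fewer. A strict same-date rule could also lose a single episode sampled some days apart, because site visits are 12 weeks apart after Week 16 and unplanned examinations are allowed.

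All of this stands. It makes the timing point an addition to the plan and not the correction of an error, and it is why a window should be allowed. It does not remove the value of fixing the concurrent definition before the data are seen.

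On the classes, the one-category note shows the intent, and ties are rare. The signs could have been altered in reading the PDF, but the same sign appears for both ALT and AST. The limits as written still contradict the note and the shift table.

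**Conclusion.** Two modest points hold.

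- The composite rows are a valid conservative screen that can include non-concurrent peaks. How often is unknown. The illustrative ranges rest wholly on assumed rates and independence and make no allowance for the entry exclusions.
- The exclusive ALT/AST limits are wrong as written, with a small effect confined to exact ties.

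Three stronger readings are tempting but not supported:

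- A reader might infer that the rule manufactures a liver-injury signal, or that the hepatic conclusion turns on a count of 0 or 1. The SAP presents these rows as laboratory elevations among several liver summaries and attaches no conclusion to them.
- A reader might take 5% to 13% as the chance of a false composite. That is an assumed-rate figure for the TBL > 1.5x row; the same method gives about 1% to 5% for TBL > 2x.
- A reader might call the ALT-only eDISH axis an error because an AST-driven composite case would plot outside the upper right quadrant. The axis is a stated definition, and such a case is still counted in the composite and cumulative ALT-or-AST rows.

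**What to change.** 1. Keep both composite rows and label them as not necessarily concurrent, as the eDISH text already does.
2. Under each, add a pre-specified count in which the bilirubin criterion is met on the same collection date as the ALT/AST elevation or within a short window whose length the SAP states in advance.
3. Rewrite the exclusive ALT/AST classes as > ULN to ≤ 3x, > 3x to ≤ 5x, > 5x to ≤ 10x, > 10x to ≤ 20x, and > 20x, as in the shift table.
4. Use one convention at the limits for the cumulative, exclusive, composite and shift categories. If only the exclusive classes change, they will disagree at ties with the cumulative rows, which use ≥.
5. At most, add an eDISH footnote identifying any AST-driven composite case.

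The cost is SAP wording and two extra table rows. The data come from the existing chemistry panel.
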